### 3.3.6. Body Mass Index (BMI) and modified Body Mass Index (mBMI)

- Change from baseline in BMI and mBMI

BMI is calculated as Weight (kg) / Height (m) ^2. mBMI is calculated by multiplying BMI (kg/m^2) by serum albumin level (g/L).

Height will be measured at screening. Weight will be measured at screening, baseline, Month 1, 6 and 12.

## 3.4. Other Endpoints (Efficacy Endpoints)

- Change from Baseline in cardiac troponin I

Cardiac troponin T (cTnT) and cardiac troponin I (cTnI) were recognized as markers of myocardial damage, Troponin T or troponin I or both may be chronically elevated in cardiac amyloidosis. Cardiac troponin I is thought to be more accurate in assessment of myocardial damage. In the appropriate clinical context of a thickened ventricle and heart failure, an elevated troponin value (outside of an acute coronary syndrome) should trigger suspicion for cardiac amyloidosis.

Blood sample collection will be performed at baseline, Month 6 and 12 for evaluation of cardiac troponin I.

- Change from Baseline in New York Heart Association (NYHA) classification

The NYHA functional classification is used to describe the functional capacity of adults with congenital heart disease to describe the severity of symptoms and exercise intolerance.

NYHA functional classification will be assessed at screening, baseline, Month 6 and 12.

### 3.5. Baseline Variables

- Demographic characteristics
- Basic disease diagnosis
- Medical history
- Serology

## 4. ANALYSIS SETS (POPULATIONS FOR ANALYSIS)

Participant Analysis Set	Description
Enrolled	All participants who sign the ICD
Safety	All enrolled participants who take at least 1 dose of tafamidis free acid 61 mg soft capsule
Efficacy	The same as the above safety analysis set
Pharmacokinetic (PK)	All safety population who have at least 1 quantifiable plasma tafamidis concentration
Pharmacodynamic (PD)	All safety population who have at least 1 TTR concentration/stabilization value

## 5. GENERAL METHODOLOGY AND CONVENTIONS

### 5.1. Hypotheses and Decision Rules

This is an estimation study with no statistical hypothesis nor decision rules.

### 5.2. General Methods

#### 5.2.1. Analyses for Continuous Endpoints

The data for all continuous endpoints will be summarized by time point in tables containing descriptive statistics (N, mean, standard deviation, standard error of the mean, minimum, 1st, 2nd (median) and 3rd quartiles and maximum) for baseline and change from baseline for those endpoints measured at baseline.

For analyses of PK continuous endpoint of tafamidis concentration, PD continuous endpoints of TTR concentration and percent stabilization (as well as TTR tetramer concentration and FOI used to calculate percent stabilization), percent coefficient of variation (CV%) was used in descriptive statistics instead of standard error of the mean.

### **5.2.2. Analyses for Categorical Endpoints**

The data for categorical endpoints (including binary) will be summarized by contingency tables that show the counts/frequency and percentage in the various categories at each time point. For some categorical endpoints, such as the presence or severity of adverse events, contingency or frequency tables will consider the data over the entire duration of the study and will not be constructed at each time point.

The 2-sided 90% confidence interval for the proportion estimate will be calculated with Clopper-Pearson exact method.

### **5.3. Methods to Manage Missing Data**

For safety data, missing dates and severity of adverse events will be imputed following Pfizer Reporting Standards. No imputation will be done for missing vital signs, ECG, Echocardiography, laboratory and physical examination measurements.

For the KCCQ-OS, SF-12 and EQ-5D-5L instruments, rules suggested by the developers of these will be followed in calculating scores when individual question/items may be missing. If these rules are not enough for calculating a score, then the endpoint will be considered to have a missing value. Missing values in any of the endpoints will not be imputed when summarizing these endpoints using descriptive statistics.

No imputation will be done for 6-MWT, NT-proBNP, tafamidis concentration, TTR stabilization and TTR concentration. Values <LLOQ will be imputed as  $\frac{1}{2}$  LLOQ.

## **6. ANALYSES AND SUMMARIES**

All efficacy and safety analyses will base on safety population. The analysis for PD endpoints (TTR stabilization and TTR concentration) will base on PD population. PK analysis will base on PK population. Refer to [Section 4](#) for population definition.

### **6.1. Primary Endpoint(s)**

#### **6.1.1. Incidence of Treatment Emergent Adverse Events**

TEAEs will be summarized according to Pfizer Reporting Standards. The summary tables of TEAE and TEAE by System Organ Class (SOC) will be provided. The incidence and severity of TEAE will be presented by SOC and MeDRA Preferred Term (PT). Incidence of serious adverse events and TEAEs that cause withdrawal will be summarized. All adverse events will be listed.

### **6.2. Secondary Endpoint(s)**

For the efficacy endpoints in [Section 3.2.1](#), PD endpoints in [Section 3.2.3](#) and quality of life endpoints in [Section 3.2.4](#), the analysis method described in [Section 5.2.1](#) and Section 5.2.2 will be followed, i.e. the basic summary statistics will be calculated by analysis visit. The estimates over time will be plotted graphically. The individual values will be listed.

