Documentation of vital status		X	X	X	X	X	X	
Record time of dosing		X	X		X		X	
Record dosing adherence			X		X		X	
Dispense investigational drugs		X	X		X			

- Visits, if applicable, are typically defined with respect to the Baseline visit and in accordance with expectations on the standard of care and/or required procedures for the study.
- Systolic and diastolic blood pressure (semisupine at least 5 minutes prior to assessment), pulse rate, respiratory rate and body temperature
- Biopsy or radionuclide bone scintigraphy (99mTc-PYP) for amyloid documentation must be performed at Screening or have been performed and documented within 5 years of enrollment. If greater than 5 years, biopsy or radionuclide bone scintigraphy (99mTc-PYP) must be repeated at the investigative site.
- Refer to [Appendix 4](#) for Contraceptive Guidance and Collection of Pregnancy Information.
- For women of childbearing potential. Refer to [Appendix 4](#) for Woman of Childbearing Potential (WOCBP).
- For those absence of a variant TTR genotype, absence of radionuclide bone scintigraphy (99mTc-PYP) and presence of amyloid deposits in biopsy tissue.
- Repeat not required if there is documentation of genotyping result confirming the TTR gene mutation within 5 years of enrollment.
- TTR stabilization and TTR concentration: baseline (Day 1) sample: collect pre-dose during the clinic visit. Month 1 sample: collect pre-dose and at 3 hours (±1.5 hours) post-dose. Month 6 sample: collected at

Procedure/ Assessment	Screening	Baseline visit	Month a					
			1 (±1 wee k)	3 (Tel eph one visit ±2 wee ks)	6 (±2 week s)	9 (Tel eph one visit ±2 wee ks)	12 (±2 weeks) (or within 2 weeks after End of Treatment)	Post- treatment follow-up (28+7 days after last dose)
	Day-45 to Day 0	Day 1						

7 hours (±2.5 hours) post-dose. Month 12 sample: collect at 1 hour (±30 minutes) post-dose, or End of Treatment sample: collect at time during the clinic visit. Please refer to [Section 8.6](#) for details.

- i. Tafamidis concentrations: Month 1 tafamidis concentration sample: collect pre-dose and at 3 hours (±1.5 hours) post-dose; Month 6 tafamidis concentration sample: collect at 7 hours (±2.5 hours) post-dose; Month 12 sample: collect at 1 hour (±30 minutes) post-dose, or End of Treatment sample: collect at time during the clinic visit. Please refer to [Section 8.5](#) for details.
- j. Kansas City Cardiomyopathy Questionnaire (KCCQ) should be completed before the EQ-5D-5L.

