In order to calculate molar ratios at various tafamidis exposures, a TTR concentration must be assumed. Mean TTR concentrations observed at baseline in Study Fx-005 (B3461020) (24.7 mg/dL) and in patients with V122I mutations in Study Fx1B-201 (13.5 mg/dL) and the Transthyretin Amyloid Cardiac Study (TRACS) (14.9 mg/dL) are assumed for the calculations that follow: a 20 mg QD tafamidis dose at steady state produces a mean MR in the range of 1.2 to 3.2 from mean minimum drug concentration at steady state ( $C_{min,ss}$ ) to maximum drug concentration at steady state ( $C_{max,ss}$ ), which is below the plateau region of the data depicted in ([Figure 1](#)). Mean  $C_{min,ss}$  to  $C_{max,ss}$  following tafamidis doses of 80 mg are expected to produce MR values of 3.5 to 9.6, which are approaching or on the plateau region of TTR % stabilization.

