### **6.2.2. PK Endpoint(s)**

Plasma concentrations of tafamidis will be summarized graphically and with descriptive statistics (N, number of participants with observations above lower limit of quantification [NALQ], arithmetic mean, standard deviation, CV%, median, and minimum and maximum) by visit and nominal time. Due to the sparse nature of the pharmacokinetic sampling scheme, a population approach may be used for pharmacokinetic data analysis. Nonlinear mixed-effect modeling may be performed to characterize the pharmacokinetics of tafamidis. If appropriate, these pharmacokinetic data may be used for exposure-response analyses. These analyses results, if conducted, will not be included in CSR but will be reported separately.

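### The planned PD summaries and plot by visit cannot separate time on study from time after dose, and one of the two Month 1 PD samples may be dropped

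*SAP*

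**What the plan says.** SAP 6.2 sets one rule for the efficacy, PD and quality-of-life endpoints: "the basic summary statistics will be calculated by analysis visit. The estimates over time will be plotted graphically". Individual values are also listed. Protocol 9.4.2 likewise summarizes the continuous PD measures by visit.

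The PD sampling times are in the notes to the Schedule of Activities (Protocol 1.3):
- Baseline: "TTR stabilization and TTR concentration: baseline (Day 1) sample: collect pre-dose during the clinic visit".
- Month 1: "Month 1 sample: collect pre-dose and at 3 hours (±1.5 hours) post-dose".
- Months 6 and 12: "7 hours (±2.5 hours) post-dose. Month 12 sample: collect at 1 hour (±30 minutes) post-dose".
- End of Treatment: any time during the clinic visit.

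Tafamidis is sampled at the same post-baseline times. SAP 6.2.2 summarizes it "by visit and nominal time", and Appendix 1.1 gives it windows in hours. PD gets windows in days only. Where several observations fall in one window, Appendix 1.1 keeps the one closest to the target day and settles ties by taking the later visit.

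Protocol 6.1.1 calls the actual dosing time essential for analysing the TTR samples as well as the PK samples.

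**The concern.** A plot of PD estimates at Months 1, 6 and 12 invites the reader to see a course of effect over a year of treatment. Here each visit also stands at its own time after the dose. A fall or rise between visits could reflect a real change, the sampling time, or both, and nothing in the planned output tells them apart. The SAP handles this for tafamidis by adding nominal time to the summary, but not for PD measured at the same times.

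Month 1 adds a second problem. It is the only visit with two PD samples, and so the only place where a post-dose difference can be seen within a visit. Both samples fall on the same study day, and the rule for choosing one observation per window cannot choose between them.

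**Working it through.** The plan gives no figure of its own on this point to reproduce. The check has three parts.

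**1. Do any visits share a post-dose time?** Windows from the Schedule of Activities:
- Month 1, post-dose: 3 ± 1.5 h = 1.5 to 4.5 h
- Month 6: 7 ± 2.5 h = 4.5 to 9.5 h
- Month 12: 1 ± 0.5 h = 0.5 to 1.5 h

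Every pair overlaps by 0 h. The windows only touch, at 1.5 h and at 4.5 h. The Month 1 pre-dose time is not repeated at a later visit.

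**2. What can be estimated?** Write each cell mean as a visit effect v plus a post-dose-time effect t:
- Month 1 pre-dose: v1 + t(pre)
- Month 1, 3 h: v1 + t(3)
- Month 6, 7 h: v6 + t(7)
- Month 12, 1 h: v12 + t(1)

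Month 12 minus Month 6 is then (v12 − v6) + (t(1) − t(7)). Adding any constant to v12 and subtracting it from t(1) leaves every cell mean unchanged, so v12 − v6 is not estimable. The same holds for Month 12 against Month 1.

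One contrast is free of this: Month 1 at 3 h minus Month 1 pre-dose = t(3) − t(pre). A rank check of the design agrees. With four cells the rank is 4 and only this contrast is estimable of the three checked. With one observation kept per visit the rank is 3 and this contrast is lost too. With a common sampling time at all visits, v12 − v6 would be estimable.

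**3. How large could it be?** Protocol 2.2.1 says that "doses of 80 mg are expected to produce MR values of 3.5 to 9.6" between the steady-state minimum and maximum, using TTR concentrations of 13.5, 14.9 and 24.7 mg/dL.
- Molar-ratio range: 9.6 / 3.5 = 2.74-fold
- TTR range: 24.7 / 13.5 = 1.83-fold
- If the lowest ratio used the highest TTR and the highest ratio the lowest TTR, the drug swing is 2.74 / 1.83 = 1.50-fold. The same step on the 20 mg figures gives (3.2 / 1.2) / 1.83 = 1.46-fold.

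The pairing is an assumption, because the protocol does not say how the extremes were formed. The result is a full trough-to-peak exposure ratio, not the 7 h to 1 h contrast.

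For that contrast, an illustrative one-compartment oral model at steady state was run with assumed half-lives of 1 to 5.6 days and absorption rates of 0.2 to 1.0 per hour. Neither range is in the documents. The ratio of drug concentration at 7 h to that at 1 h came out between 1.01 and 1.24.

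None of this converts to percent stabilization, because the concentration-stabilization curve (Protocol Figure 1) is not shown in the text available.

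**The case against.** The strongest reply is that the study is purely descriptive. There is no hypothesis or decision rule (Protocol 9.1, SAP 5.1), the objective is to characterize PD, and no planned analysis estimates a change from Month 6 to Month 12. The plot stands beside summaries, the responder proportion with its interval, and listings. Dosing and sampling times are recorded, so later adjustment is possible. All of this is true, and it limits the harm to how a figure and its tables are read. It does not make the time axis mean what it appears to mean.

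A second reply is that SAP 5.2.1 and 5.2.2 speak of summaries by time point, which could cover nominal time. But SAP 6.2 spells out the method as by analysis visit, and Appendix 1.1 gives PD no hour windows. At best the text is ambiguous about Month 1.

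A third is that PK/PD modelling will deal with it. SAP 6.2.2 makes population PK and exposure-response analyses optional and reports them outside the CSR.

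The reply on size stands. The protocol places this dose approaching or on the plateau, where exposure matters less. Protocol 4.3 reports a simulated fed-to-fasted difference in steady-state peak of only about 2%, which fits a fairly flat profile. No figure is given for variation in TTR concentration within a day.

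The reply on remedy also stands in part: labelling by nominal time splits only Month 1 and does not undo a confounding that the sampling schedule created.

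**Conclusion.** The structural point holds and does not depend on size: after baseline, visit and nominal post-dose time move together, so differences in PD between visits cannot be attributed to time on study. As written, the SAP may also discard one of the two Month 1 samples.

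The size for percent stabilization is unknown and may be modest. For TTR concentration the documents give nothing from which to judge it.

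A reader might infer three stronger things that the documents do not support:
- That visits could differ by 1.5-fold through sampling time alone. That figure is a trough-to-peak exposure ratio under an assumed pairing, not the Month 6 to Month 12 difference and not a PD effect.
- That the Month 12 sample sits near trough, so the plot would falsely show loss of stabilization. The documents give no time of peak and no steady-state profile, so the direction is not established.
- That the PD objective cannot be met. The objective is descriptive, and the plot is one display among several.

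**What to change.** In SAP 6.2, state that TTR stabilization and TTR concentration will be tabulated and labelled by visit and nominal post-dose time, as SAP 6.2.2 does for tafamidis. In Appendix 1.1, exempt PD from the rule of one observation per window where two samples were planned at one visit, so that both Month 1 samples are kept and shown separately. End of Treatment samples have no nominal post-dose time and need their own label.

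If a plot by visit is kept, mark the sampling time on each point and do not present it as a time course of effect. Add a plot of percent stabilization against the tafamidis:TTR molar ratio, or against tafamidis concentration, from the paired samples. This is the type of display in Protocol Figure 1.

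These changes make the sampling time visible and stop it being read as a change in effect. They do not make visit contrasts estimable. That would need a common sampling time or a model that uses actual post-dose time or tafamidis concentration.

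The cost is SAP wording, slightly more output and no single PD time-course figure. No new samples are needed.

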### **6.2.1. Safety Summaries and Analyses Endpoint(s)**

Not applicable.

### **6.2.2. PK Endpoint(s)**

Plasma concentrations of tafamidis will be summarized graphically and with descriptive statistics (N, number of participants with observations above lower limit of quantification [NALQ], arithmetic mean, standard deviation, CV%, median, and minimum and maximum) by visit and nominal time. Due to the sparse nature of the pharmacokinetic sampling scheme, a population approach may be used for pharmacokinetic data analysis. Nonlinear mixed-effect modeling may be performed to characterize the pharmacokinetics of tafamidis. If appropriate, these pharmacokinetic data may be used for exposure-response analyses. These analyses results, if conducted, will not be included in CSR but will be reported separately.

## **6.3. Other Safety Summaries and Analyses Endpoints**

### **6.3.1. Laboratory Data**

The incidence of laboratory abnormalities observed at any time during the study will be tabulated following Pfizer Reporting Standards. Summary statistics for changes from baseline in RBP will be provided by visit.

### **6.3.2. Electrocardiograms**

Centrally over-read ECG variables will be summarized by mean change from baseline to each measurement time for heart rate, PR interval, QRS interval, QT interval and QTcF (Fridericia correction) intervals. Additionally, the incidence of categorical increases in QTc intervals will be provided. Categories for QTcF are  $\geq 450$  msec,  $\geq 480$  msec, and  $\geq 500$  msec. Categories for QTcF as change from baseline are  $\geq 30$  msec increase,  $\geq 60$  msec increase and  $\geq 75$  msec increase. QTcF is considered the primary QTc value as this correction is more appropriate. In addition, the number (%) of subjects with normal, abnormal not clinically significant, abnormal clinically significant and unevaluable will also be summarized at each visit.

### **6.3.3. Echocardiograph**

The number (%) of subjects with normal, abnormal not clinically significant, abnormal clinically significant and unevaluable will be summarized at each visit. The number (%) of subjects with no baseline/screening, no significant change and significant change compared with baseline will be summarized at each visit. Summary statistics for change from baseline values will also be provided by visit.

### **6.3.4. Vital Signs**

Participants with abnormalities will be summarized by each vital sign parameter. Individual values for actual value will be listed.

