### 8.2.2. Vital Signs

Vital signs will be recorded at each study visit.

Vital signs will be measured with the participant in a semisupine position after at least 5 minutes of rest and will include body temperature, systolic and diastolic blood pressure, and pulse rate and respiratory rate. Three readings of blood pressure and pulse rate will be taken. The first reading should be rejected. The second and third readings should be averaged to give the measurement to be recorded in the CRF.

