#### **9.4.1.4. Other Safety Assessments**

All clinical laboratory data will be subjected to clinical review and summarized by frequency of events and mean changes from baseline.

All vital sign measurements will be displayed in listings by participant for each sample collection date and time with changes from baseline values included.

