### 2.1. Modifications to the Analysis Plan Described in the Protocol

[Protocol section 9.4.1.2](#) Electrocardiogram Analyses states categories for QTcF as change from baseline are:  $\geq 30$  msec increase,  $\geq 60$  msec increase. A  $\geq 75$  msec increase category is added in [Section 6.2.3.2](#) as deemed clinical important.

[Protocol section 9.4.1.4](#) Other Safety Assessments states all clinical laboratory data will be summarized by frequency of events and mean changes from baseline. This change from baseline summary will not be done as considered clinical meaningless.

Protocol section 9.4.1.4 Other Safety Assessments states all vital sign measurements will be displayed in listings by participant with changes from baseline values included. This change from baseline values will not be listed as considered clinical meaningless.

[Protocol section 9.4.2](#) states PD endpoints will also be analyzed by TTR genotype. This subset analysis will only be done if sample sizes for both TTR wild-type and variant genotype subsets allowed.

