### 3.3.4. Vital Signs

- Incidence of vital sign abnormalities

Vital sign measures include systolic blood pressure, diastolic blood pressure, pulse rate, respiratory rate, and body temperature. Vital signs will be measured at screening, baseline, Month 1, 6 and 12.

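### Blood pressure is summarized only as counts of abnormalities plus a raw listing, so a modest systematic shift would appear in no planned summary table

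*SAP*

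**What the plan says.** - **Measurement.** SAP 3.3.4 states: "Vital sign measures include systolic blood pressure, diastolic blood pressure, pulse rate, respiratory rate, and body temperature". On timing it adds: "Vital signs will be measured at screening, baseline, Month 1, 6 and 12". Protocol 8.2.2 has blood pressure and pulse read three times with the first reading rejected, and then: "The second and third readings should be averaged to give the measurement to be recorded in the CRF".
- **Endpoint.** The only vital-sign endpoint in SAP 3.3.4 is "Incidence of vital sign abnormalities".
- **Planned output.** SAP 6.3.4 says "Participants with abnormalities will be summarized by each vital sign parameter" and then provides a listing of each individual's actual values. It gives no criteria for an abnormality.
- **Protocol plan.** Protocol 9.4.1.4 asked for a listing, not a summary table: "All vital sign measurements will be displayed in listings by participant for each sample collection date and time with changes from baseline values included".
- **Departure from the protocol.** SAP 2.1 discloses the change to that listing: "This change from baseline values will not be listed as considered clinical meaningless". No further reason is given.
- **Other safety series.** Under SAP 6.3.2, ECG variables are "summarized by mean change from baseline to each measurement time for heart rate" and for the intervals. SAP 6.3.1 (RBP only), 6.3.3 (echocardiography) and 6.3.6 (BMI/mBMI) also plan summaries of change from baseline. Routine laboratory data do not get one; SAP 2.1 removes it for the same stated reason.

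**The concern.** The primary objective is to characterize the safety profile in Chinese ATTR-CM patients, and the study is one of estimation. The protocol takes care to obtain a precise blood-pressure value, yet the SAP's only summary reduces it to abnormal or not abnormal.

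The general rule in SAP 5.2.1, which gives descriptive statistics and change from baseline for continuous endpoints, does not clearly reach blood pressure, because the endpoint has been defined as an incidence. Pulse rate is partly backed up by ECG heart rate. Systolic and diastolic pressure have no such back-up. The safety report could therefore be completed as planned without any summary of the level of blood pressure or of its movement over 12 months of treatment.

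**Working it through.** **1. The plan's own figure.** The only sample-size figure is 53 treated participants, for an 80% probability of seeing at least one TEAE with a 3% incidence (protocol 9.2).
- n = ln(0.20)/ln(0.97) = 52.84, rounded up to 53.
- 1 − 0.97^53 = 0.801; with 52 participants it is 0.795.

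The figure reproduces. It does not concern blood pressure, but it supplies the n used below.

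**2. What each safety series receives in the SAP.**

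| Series | Abnormality or category counts | Change-from-baseline summary |
|---|---|---|
| ECG heart rate and intervals (6.3.2) | yes | yes |
| Echocardiography (6.3.3) | yes | yes |
| BMI/mBMI (6.3.6) | no | yes |
| RBP (6.3.1) | yes, with the laboratory data | yes |
| Routine laboratory data (2.1, 6.3.1) | yes | no |
| Vital signs, including blood pressure (2.1, 6.3.4) | yes | no, and removed from the listing |

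Blood pressure is in the same position as routine laboratory data and differs from the other four rows.

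**3. Precision available from the data already collected.** The documents give no SD for change in blood pressure, so 10 to 18 mmHg is an assumption. The 95% half-width for a mean change is t(0.975, n−1) × SD/√n. For n = 53, t is about 2.007 and √53 is about 7.280.

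| Assumed SD of change (mmHg) | Half-width, n = 53 | Half-width, n = 43 (assumed evaluable) |
|---|---|---|
| 10 | 2.8 | 3.1 |
| 12 | 3.3 | 3.7 |
| 15 | 4.1 | 4.6 |
| 18 | 5.0 | 5.5 |

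**4. How little a count may move.** This step only shows the direction of the argument, because the SAP does not state its abnormality criteria. Assume normally distributed systolic pressure, a cut-off below 90 mmHg and a uniform fall of 5 mmHg. The expected number below the cut-off is 53 × Φ((90 − mean)/SD).
- Mean 120, SD 15: 53 × Φ(−2.00) = 1.2 before the fall and 53 × Φ(−1.67) = 2.5 after it.
- Lowest case (mean 125, SD 15): 0.5 before, 1.2 after.
- Highest case (mean 110, SD 18): 7.1 before, 10.7 after.

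The 90% Clopper-Pearson intervals (the method in SAP 5.2.2) for 1, 2 and 3 of 53 are 0.1–8.6%, 0.7–11.4% and 1.6–14.0%. They overlap almost entirely. If the actual criteria include a change from baseline, this step does not represent the plan; step 3 is unaffected.

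**The case against.** The case for leaving the SAP alone has real substance.

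- **Values are listed.** A reader might infer that blood pressure is reported only as counts, or that a shift cannot be seen at all. SAP 6.3.4 does not support that: it lists actual values, so change can be derived by subtraction. What is missing is any planned output that does so.
- **Blood pressure is not a lone exception.** A reader might infer that every other continuous safety series keeps a change summary. Routine laboratory data do not; SAP 2.1 treats the two domains alike.
- **The choice is disclosed, and little was lost against the protocol.** Protocol 9.4.1.4 never planned a table of vital-sign means, and protocol section 9 allows the SAP to modify the outlined analyses. The SAP removes a derived column but adds a tabulation of abnormalities.
- **Important changes have another route.** Under protocol 10.3.1, vital-sign findings judged clinically significant, including worsening from baseline, can be recorded as adverse events and so reach the TEAE tables of SAP 6.1.1.
- **No drug effect can be isolated.** A reader might take a mean change as the effect of tafamidis. The study has one arm and participants continue their current medications, so disease course, co-medication and regression to the mean are all mixed in.
- **Power is not the right measure.** Protocol 9.1 and SAP 5.1 plan no hypothesis test, so a gain in power would describe a decision that nobody makes.

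All six points stand, and they limit the size of the concern. They do not remove it. A listing is not a summary, and adverse-event reporting depends on individual judgement, so it is not suited to showing a small shift across the group. The single-arm limit applies equally to the ECG and echocardiography changes that the SAP does summarize. The reason in SAP 2.1 is an assertion, and it sits oddly beside the change summary kept for heart rate.

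**Conclusion.** The point holds in a limited form. Blood pressure is collected as a precise continuous value but summarized only through counts of abnormalities whose criteria the SAP does not give, with a raw listing that no longer carries change from baseline. A modest systematic shift would therefore appear in no planned summary table.

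A by-visit table would describe the mean systolic change to within about ±2.8 to ±5.0 mmHg. That range rests on an assumed SD of change of 10 to 18 mmHg and on all 53 participants being evaluable; with 43 it is ±3.1 to ±5.5 mmHg. The result would be a description of change during treatment only.

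This is an inexpensive improvement to a descriptive safety output. Neither the primary endpoint nor the sample size is affected.

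**What to change.** 1. In SAP 3.3.4, add change from baseline in systolic and diastolic blood pressure as a descriptive safety endpoint beside the incidence of abnormalities.
2. In SAP 6.3.4, add by-visit descriptive statistics in the SAP 5.2.1 format for actual value and change from baseline. A 95% confidence interval for the mean change is optional, since SAP 5.2.1 specifies none for means.
3. Delete the vital-sign paragraph in SAP 2.1 and adjust the listing sentence in SAP 6.3.4, so that the listing again carries the change column of protocol 9.4.1.4.
4. Keep the abnormality counts, and state the criteria behind them.
5. Note with the table that the study is single-arm and that the figures describe change during treatment.

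The cost is SAP wording and one more descriptive table. The data are already collected, protocol 9.4 already defines baseline, and SAP Appendix 1.1 already sets analysis windows for endpoints assessed at Months 1, 6 and 12. No visit, procedure or participant is added.
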